Considering the growing evidence for aggressively treating LDL-C, even in the setting of what some might consider patients with HoFH that might be at their “goal” LDL-C (ie, 70 mg/dL), the benefits of adding evinacumab and potentially lowering the LDL-C even further become apparent. For patients entering this study from another evinacumab trial there is no LDL-C entry criterion as these patients would have been treated with evinacumab for at least 24 weeks prior to entering this study and would have achieved their maximal lipid lowering effect.

Preliminary data from the proof-of-concept study in patients with HoFH demonstrate the efficacy of evinacumab in this patient population, even in the most difficult-to-treat patients with null/null mutations in the LDLR gene. Recent data from study R1500-CL-1629 in adult and adolescent patients with HoFH demonstrated that adding evinacumab to other lipid-lowering therapies decreased LDL-C by a mean of 49% from baseline to week 24. This efficacy data was accompanied by an acceptable safety profile. AEs that occurred in at least 5% of patients and more commonly with evinacumab were influenza-like illness (11% evinacumab, 0% placebo) and rhinorrhea (7% evinacumab, 0% placebo). The accumulated safety information from the completed and ongoing clinical studies had identified the risk of systemic hypersensitivity reactions (including anaphylaxis and infusion reactions). The important potential risks (based on preclinical evaluation or risks associated with monoclonal antibodies in general) include embryofetal toxicity and immunogenicity. These risks will be managed through careful patient selection, routine monitoring, and complete disclosure of safety information.

Patients entering this study should be on a stable background LMT, which may or may not include a statin, ezetimibe, and a PCSK9 inhibitor. There are 2 PCSK9 inhibitors that are commercially available in many countries; evolocumab is approved for use in patients with HoFH in most countries, and alirocumab is currently being evaluated in a phase 3 double-blind placebo-controlled study in patients with HoFH (study R727-CL-1628, ODYSSEY HoFH). Patients entering this study may be taking either evolocumab or alirocumab. Patients who complete study R727-CL-1628 (ODYSSEY HoFH) with alirocumab are permitted to participate in this study and may continue to receive alirocumab as part of their background LMT.

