9.4.3. Other Events that Require Accelerated Reporting to Sponsor

The following events also require reporting to the sponsor (or designee) within 24 hours of learning of the event:

Symptomatic Overdose of Study Drug: Accidental or intentional overdose of at least 2 times the intended dose of study drug within the intended therapeutic window, if associated with an AE,

Pregnancy: Although pregnancy is not considered an AE, it is the responsibility of the investigator to report to the sponsor (or designee), within 24 hours of identification, any pregnancy occurring in a female patient or female partner of a male patient, during the study or within 24 weeks of the last dose of study drug. Any complication of pregnancy affecting a female study patient or female partner of a male study patient, and/or fetus and/or newborn that meets the SAE criteria must be reported as an SAE. Outcome for all pregnancies should be reported to the sponsor.

Adverse Events of Special Interest: All AESI, serious and nonserious, must be reported within 24 hours of identification using the same reporting process as for SAE reporting, per Section 9.4.2.

Adverse events of special interest for evinacumab include the following:

- Anaphylactic reactions
- Moderate or severe infusion reactions

- Increase in ALT or AST: ≥ 3 x ULN (if baseline <ULN), or ≥ 2 times the baseline value (if baseline \geq ULN)
- Allergic events and/or local injection site reactions that require medical treatment or that require consultation with another physician for further evaluation
- Pregnancy
- Symptomatic overdose with investigational medicinal product
- Neurocognitive events
- New onset of diabetes*
- Pancreatitis

Adverse events of special interest for alirocumab include the following:

- Increase in ALT: ALT ≥ 3 x ULN (if baseline ALT <ULN), or ALT ≥ 2 times the baseline value (if baseline ALT \geq ULN)
- Allergic events and/or local injection site reactions that require consultation with another physician for further evaluation
- Pregnancy
- Symptomatic overdose with investigational medicinal product
- Neurologic events that require additional examinations/procedures and/or referral to a specialist
- Neurocognitive events
- Cataracts
- New onset of diabetes*

*New onset of diabetes is defined as any of the following:

- Type 1 or type 2 diabetes TEAE (grouping of MedDRA terms will be specified in the statistical analysis plan [SAP])

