9.5. Evaluation of Severity and Causality

9.5.1. Evaluation of Severity

The severity of AEs will be graded according to the following scale:

Mild: Does not interfere in a significant manner with the patient normal functioning level. It may be an annoyance. Prescription drugs are not ordinarily needed for relief of symptoms, but may be given because of personality of the patient.

Moderate: Produces some impairment of functioning but is not hazardous to health. It is uncomfortable or an embarrassment. Treatment for symptom may be needed.

Severe: Produces significant impairment of functioning or incapacitation and is a definite hazard to the subject's health. Treatment for symptom may be given and/or patient hospitalized.

If a laboratory value is considered an AE, its severity should be based on the degree of physiological impairment the value indicates.

Infusion Reactions

The severity of infusion reactions will be graded according to the following scale (semi-colon indicates “or” within description of the grade):

Mild: Mild transient reaction; infusion interruption not indicated; intervention not indicated.

Moderate: Therapy or infusion interruption indicated but responds promptly to symptomatic treatment (eg, antihistamines, NSAIDs, narcotics, IV fluids); prophylactic medications indicated for ≤ 24 hours.

Severe: Prolonged (eg, not rapidly responsive to symptomatic medication and/or brief interruption of infusion); recurrence of symptoms following initial improvement; hospitalization indicated for clinical sequelae; life-threatening consequences; urgent intervention indicated; death.

Injection Site Reactions

The severity of injection site reactions will be graded according to the following scale (semi colon indicates “or” within description of grade):

Mild: Pain that does not interfere with activity; mild discomfort to touch; < 5 cm of erythema or induration that does not interfere with activity.

Moderate: Pain that requires repeated use of non-narcotic pain reliever > 24 hours or interferes with activity; discomfort with movement; 5.1 cm to 10 cm erythema or induration or induration that interferes with activity.

Severe: Pain that requires any use of narcotic pain reliever or that prevents daily activity; significant discomfort at rest; > 10 cm erythema or induration; prevents daily activity; requires ER visit or hospitalization; necrosis or exfoliative dermatitis.

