10.4.4.1. Adverse Events

Definitions

For safety variables, the following observation periods are defined:

- The pretreatment period is defined as the time from signing the ICF to before the first dose of study drug
- The open-label TEAE period is defined from the day of the first open-label study treatment administration to the day of the last open-label study treatment administration + 168 days
- The post-treatment period is defined as the time from the day after the end of the respective TEAE periods to the last study visit

Open-label TEAEs are defined as those events that developed, worsened, or became serious during the open-label TEAE period.

Analysis

All AEs reported in this study will be coded using the currently available version of the Medical Dictionary for Regulatory Activities (MedDRA®). Coding will be to lowest level terms. The verbatim text, the preferred term (PT), and the primary system organ class (SOC) will be listed.

Adverse event incidence tables will present data by SOC sorted alphabetically and PT sorted by decreasing frequency, and summarize the number (n) and percentage (%) of patients experiencing an AE. Multiple occurrences of the same event in the same patient will be counted only once in the tables. Data conventions for missing or partial AE dates will be addressed in the SAP. The denominator for computation of percentages is the respective SAF by the status of previous evinacumab treatment exposure, and again for the subpopulation of adolescent patients [yes/no].

Summaries of all TEAEs will at least include:

- All TEAEs (and patient listing)
- All treatment-emergent SAEs, including patient deaths (and patient listing)
- Treatment-emergent AESIs (eg, hypersensitivity and anaphylaxis, defined by a pre-specified grouping) (Section 9.4.3)
- TEAEs by severity (according to the grading scale outlined in Section 9.5.1), presented by SOC and PT, depicting the worse TEAE severity for those patients with multiple occurrences of the same event)
- All TEAEs leading to permanent treatment discontinuation (and patient listing)

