4.8.1.2. Adverse Events of Special Interest

Adverse events of special interest (AESI) are AEs (serious or non-serious) required to be monitored, documented, and managed in a pre-specified manner. AESIs will be recorded on the adverse event e-CRF using dedicated tick boxes, and/or identified using standard MedDRA queries (SMQ), company MedDRA queries (CMQ), MedDRA terms, and/or applicable laboratory assessments. Appendix 10.3 contains the definitions used to identify AESIs:

The AESIs include:

- Anaphylactic reactions (e-CRF)
- General allergic events (SMQ)
- Infusion reactions (e-CRF)
- Hepatic Disorder (SMQ, lab data)
- Pregnancy (e-CRF)
- Symptomatic overdose with investigational medicinal product (e-CRF)
- Neurocognitive events (CMQ)
- Neurologic events (e-CRF)
- New onset of diabetes (NOD) (lab data, MedDRA HLT, concomitant medications) for patients without diabetes mellitus at baseline
- Diabetic complication (CMQ, concomitant medications) for patients with diabetes mellitus at baseline
- Pancreatitis (e-CRF)
- Cataracts (MedDRA HLT)
- Immune complex diseases (SMQ)
- Muscle events/CK elevation (MedDRA SOC, SMQ, lab data)

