5.8.2. Analysis of Adverse Events of Special Interest

- Treatment-emergent adverse events of special interest (AESI), as listed in Section 4.8.1.2, will be presented by SOC and PT as applicable. AESI are defined by SMQ, CMQ, and/or dedicated e-CRF as described in Appendix 10.3 .

The following variables will also be tabulated for infusion reactions TEAEs:

- Intensity of the event (mild, moderate, severe or very severe);
- Number of events divided by the number of study treatment administrations received in treatment period;
- Time from first study treatment to first infusion reaction;

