10.3. List of AESIs with Data Sources and Definitions of SMQ/CMQ

Table 2: Summary of AESIs and the Methods of Data Collections and Derivations

AESI	Using an e-CRF specific tick box on AE page	Using Standard MedDRA Query (SMQ)/company MedDRA Query (CMQ) or lab data
Anaphylactic reactions	Yes	No
General allergic events	No	SMQ “hypersensitivity” (broad and narrow) excluding the following preferred terms linked to local injection site reactions (“infusion site dermatitis”, “infusion site hypersensitivity”, “infusion site rash”, “infusion site urticaria”, “injection site dermatitis”, “injection site hypersensitivity”, “injection site rash”, “injection site urticaria”, “injection site vasculitis”) plus “idiopathic angioedema”
Infusion reactions	Yes	No
Hepatic Disorders	No	
 • SMQ Drug-related hepatic disorder • Potentially clinically significant value (PCSV) in Appendix 10.4 • Hy’s law eDISH plot
Pregnancy	Yes	No
Symptomatic overdose with investigational medicinal product	Yes	No
Neurocognitive events	Yes	
 • CMQ for neurocognitive events as defined based on Regulatory Agency request for another lipid lowering program (See Table 3 in Appendix 10.3 for the list of terms)
Neurologic events	Yes	No

AESI	Using an e-CRF specific tick box on AE page	Using Standard MedDRA Query (SMQ)/company MedDRA Query (CMQ) or lab data

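### The SAP has no AESI group for local infusion or injection site reactions, which the protocol makes an AESI, and it grades infusion reactions on a four-level scale where the protocol has three levels

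*SAP*

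**What the plan says.** Protocol 9.4.3 lists among the evinacumab AESIs "Allergic events and/or local injection site reactions that require medical treatment or that require consultation with another physician for further evaluation". The alirocumab list in the same section has a narrower item: there, only the need for another physician's evaluation triggers it. Every AESI, serious or not, must reach the sponsor within 24 hours.

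SAP 4.8.1.2 names 14 AESIs. The allergy-related ones are "Anaphylactic reactions (e-CRF"), "General allergic events (SMQ") and infusion reactions by e-CRF. None is for local site reactions. SAP 10.3 Table 2 defines general allergic events as the hypersensitivity SMQ, broad and narrow, "excluding the following preferred terms linked to local injection site reactions", and then names four infusion-site and five injection-site terms.

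For infusion reactions, SAP 5.8.2 tabulates "Intensity of the event (mild, moderate, severe or very severe"). Protocol 9.5.1 grades them mild, moderate or severe, and its severe level already includes "hospitalization indicated for clinical sequelae; life-threatening consequences; urgent intervention indicated; death". SAP 1.2.3 declares no change from the protocol.

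**The concern.** Safety is the primary endpoint, and the AESI tables are where a reader looks for events that the sponsor singled out in advance. An analyst who follows the SAP exactly would produce AESI output that omits events the protocol defines as AESIs and that sites had to report within 24 hours. The omission cannot be seen in the tables themselves, because the excluded terms are not collected anywhere under a local-reaction heading.

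The severity point is smaller. A level that the protocol never defines gives a row that says nothing if sites grade by the protocol. A reader who does not go back to protocol 9.5.1 could take an empty 'very severe' row as information about the worst reactions, when those sit in the row above.

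**Working it through.** The plan has no figure to reproduce here. The check is a comparison of definitions and some counting.

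**Step 1. Local site reactions.**

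| Question | Protocol | SAP |
|---|---|---|
| Is there a local-reaction AESI? | Yes, in 9.4.3, for both drugs, with different triggers | No; 0 of 14 in 4.8.1.2 |
| Where do the terms go? | – | 4 infusion-site + 5 injection-site = 9 terms removed from general allergic events; no local-reaction group receives them |
| Declared as a change? | – | No (1.2.3) |

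The protocol item speaks of injection site reactions, while evinacumab is infused. That does not take infusion-site terms outside the item as the SAP reads it: Table 2 itself describes all nine, the four infusion-site terms included, as linked to local injection site reactions.

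**Step 2. Other routes into an AESI table.** Protocol 9.3.4 defines an infusion reaction as a relevant AE during the infusion or within 2 hours after it. A local reaction in that window may be caught by the infusion-reaction tick box. Two kinds of event are left over:

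- an infusion-site urticaria that starts the day after dosing and needs treatment. It meets the evinacumab criterion, falls outside the 2 hours, and its preferred term is one of the nine;
- an injection site reaction to sponsor-supplied subcutaneous alirocumab that needs another physician's evaluation. It meets the alirocumab criterion and has no link to the infusion unless the timing happens to coincide.

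Both appear in the all-TEAE tables of SAP 5.8.1 by system organ class and preferred term. Neither has a local-reaction AESI table.

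**Step 3. Severity levels.** Protocol 9.5.1 has 3 levels for infusion reactions and SAP 5.8.2 has 4. SAP 5.8.1 uses 3 for all TEAEs, so the SAP also differs from itself. If sites can record only the protocol's levels, the count in the fourth row is 0 for any data. There is a knock-on effect: SAP 6.3 classes a missing intensity as severe. That is the worst case on three levels but not on four.

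**Step 4. Scale.** The documents give no expected number of events. One affected patient is 1/120 = 0.8% of the planned total, or 1/14 = 7.1% of the planned adolescents, whose safety is a primary objective of its own.

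**The case against.** The strongest reply is that nothing is lost. The events remain in the all-TEAE tables by preferred term and severity, and in the serious and discontinuation tables where they qualify. The protocol item is a combined one, and its allergic half is covered by the hypersensitivity SMQ. A life-threatening or fatal infusion reaction is an SAE and appears in the serious TEAE tables and listings; a fatal one also appears among TEAEs leading to death. All of this stands. It limits the point to AESI output and does not supply the missing group.

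A reader might infer that the plan under-counts the drug's identified risk. The documents do not support that. Protocol 3.2.3 says that accumulated data "had identified the risk of systemic hypersensitivity reactions (including anaphylaxis and infusion reactions"). That risk is systemic, and taking local terms out of a systemic allergy group is consistent with it. The gap is that the local terms then have no group of their own.

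A reader might also infer that finding anaphylaxis by tick box alone contradicts the protocol. Protocol 10.4.4.1 plans "Treatment-emergent AESIs (eg, hypersensitivity and anaphylaxis, defined by a pre-specified grouping"), but that is an example naming both conditions together, and the SAP does pre-specify an SMQ for general allergic events. An un-ticked anaphylaxis would still appear by preferred term, and nothing in the documents shows that cases go un-ticked.

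Version lag is possible. The SAP is a first version signed on 31 October 2019, with the schedules of Amendments 5A and 5B, and the protocol is later. The Amendment 6 log records moderate-to-severe infusion reactions as an added AESI and does not mention local reactions, so lag is neither shown nor excluded. In either case the SAP has to match the current protocol before database lock.

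**Conclusion.** The point holds on two items. The SAP gives no AESI group to local infusion or injection site reactions, which protocol 9.4.3 makes an AESI, and it removes nine site-reaction terms from general allergic events without giving them a local-reaction group. It also tabulates infusion reactions on a scale that the protocol does not use.

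The effect is on where events are displayed and how they are labelled; no event disappears from the safety report. It is still worth correcting, because these tables report the primary endpoint and the correction is small.

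The conclusion depends on the following:

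- That the fourth severity row is always empty assumes an e-CRF that follows protocol 9.5.1. The e-CRF is not among the documents, so it would be too strong to say that no site can record 'very severe'.
- One of the nine terms, injection site vasculitis, might be picked up by the narrow vasculitis SMQ under immune complex diseases. That cannot be checked without MedDRA, and it would not amount to a local-reaction group.
- The number of affected events is unknown, so no bias in an incidence can be stated.

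**What to change.** 1. In SAP 4.8.1.2 and 10.3 Table 2, add an AESI group for local infusion/injection site reactions, with a fixed list of infusion-site and injection-site terms that includes the nine now excluded. Within it, identify events that met the protocol 9.4.3 criteria, using the separate triggers for evinacumab and alirocumab, from the AESI reports where this is recorded. Table 2 shows no tick box for local reactions and no document shows a field for consultation, so this second part may be incomplete and the table should say so.
2. In SAP 5.8.2, tabulate infusion reactions as mild, moderate or severe. List separately the severe ones that meet the life-threatening or fatal SAE criteria. The rule in SAP 6.3 for missing intensity then gives the worst level again.
3. If the sponsor prefers to keep either difference, state it with a reason in SAP 1.2.3.

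An anaphylaxis MedDRA grouping beside the tick box would be a useful cross-check, as the SAP already does for neurocognitive events. It is optional and corrects no error.

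The cost is one more table, a short listing and some medical review. No new visits or assessments are needed. The term list should be fixed before database lock.

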6.2.2. Exclusion Criteria for Evinacumab-Naïve Patients

A patient who meets any of the following criteria will be excluded from the study:

1. Concomitant medications and procedures that have not been stable prior to the baseline visit (see Section 7.7.2 for medications and procedures and their associated required duration of therapy).
2. Any new condition or worsening of an existing condition, which in the opinion of the investigator would make the patient unsuitable for enrollment, or could interfere with the patient participating in or completing the study.
3. History of a MI, unstable angina leading to hospitalization, coronary artery bypass graft surgery, percutaneous coronary intervention, uncontrolled cardiac arrhythmia, carotid surgery or stenting, stroke, transient ischemic attack, valve replacement surgery, carotid revascularization, endovascular procedure or surgical intervention for peripheral vascular disease within 3 months prior to the baseline visit.
4. Presence of any clinically significant uncontrolled endocrine disease known to influence serum lipids or lipoproteins.

Note: patients on thyroid replacement therapy can be included if the dosage of replacement therapy has been stable for at least 12 weeks prior to screening and the thyroid stimulating hormone (TSH) level is within the normal range of the central laboratory at the screening visit.

5. Newly diagnosed (within 3 months prior to screening visit diabetes mellitus or poorly controlled (HbA1c >9%) diabetes.
6. Use of systemic corticosteroids, unless used as replacement therapy for pituitary/adrenal disease with a stable regimen for at least 6 weeks prior to screening visit.

Note: topical, intra-articular, nasal, inhaled and ophthalmic steroid therapies are not considered as 'systemic' and are allowed.
7. Use of estrogen or testosterone therapy unless the regimen has been stable 6 weeks prior to the screening visit and no plans to change the regimen during the study.
8. Systolic blood pressure >160 mmHg or diastolic blood pressure >100 mmHg at the screening visit.
9. History of cancer within the past 5 years, except for adequately treated basal cell skin cancer, squamous cell skin cancer, or in situ cervical cancer.
10. History of New York Heart Association (NYHA) Class IV heart failure within 12 months before screening.

11. Laboratory findings during the screening period (applies to patients undergoing Screening):

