- Analyses performed according to diabetes status will be done considering diabetic patients as patients with either type 1 or type 2 diabetes in the medical history e-CRF page (regardless of the ongoing status).

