New onset of diabetes (NOD) for patients without diabetes mellitus at baseline	No	
No medical history of diabetes as specified in Cardiovascular History and Cardiovascular Risk Factors and Medical History CRF pages, AND Hb1Ac < 6.5% at baseline
 
AND one of the following:
 
Lab criteria: At least 2 values of HbA1c \geq6.5% during the TEAE period. NOTE: For patients with only a single measurement available during the TEAE period, a single value \geq6.5% will be considered and qualify the patient as NOD by default. For patients with several HbA1c measurements but only with the last one \geq6.5%, this single value \geq6.5% will be considered and qualify the patient as NOD by default.
 
OR
 
Lab criteria: At least 2 values of fasting glucose \geq126 mg/dL (7.0 mmol/L). NOTE: For patients with only a single measurement available during the TEAE period, a single value \geq126 mg/dL (7.0 mmol/L) will NOT be considered and will NOT qualify the patient as NOD. For patients with several fasting glucose measurements but only with the last one \geq126 mg/dL (7.0 mmol/L), this single value \geq 126 mg/dL (7.0 mmol/L) will NOT be considered and will NOT qualify the patient as NOD.
 
OR
 
HLT Diabetes mellitus (including subtypes)
 
OR
 
- Initiation of any new concomitant medication for hyperglycemia during the treatment period

Diabetic complication for patients with diabetes mellitus at baseline	No	For patients with medical history of diabetes as specified in Cardiovascular History and Cardiovascular Risk Factors and Medical History CRF pages, each of the following criteria will be considered, respectively:

AESI	Using an e-CRF specific tick box on AE page	Using Standard MedDRA Query (SMQ)/company MedDRA Query (CMQ) or lab data
		
 • Diabetes mellitus or diabetic complication TEAEs using HLTG Diabetic complications, HLT Diabetes mellitus (incl subtypes), and PTs Blood glucose increases, Glycosylated haemoglobin increased, Hyperglycaemia, Hyperglycaemic unconsciousness, and Hyperglycaemic seizure • Changes in diabetic medication dosage (specifically increases in dosage) or initiation of additional diabetic medication
Pancreatitis	Yes	No
Cataracts	No	HLT Cataract conditions
Immune complex diseases	No	SMQ (Narrow) Systemic lupus erythematosus SMQ (Narrow) Vasculitis SMQ (Narrow) Guillain-Barre syndrome

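### SAP Table 2 places a patient with no recorded diabetes and a baseline HbA1c of 6.5% or more in neither of its two diabetes AESIs

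*SAP*

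**What the plan says.** SAP Appendix 10.3, Table 2 sets an entry condition for each diabetes AESI before any event criterion applies.

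- New onset of diabetes: no history of diabetes on the cardiovascular and "Medical History CRF pages, AND Hb1Ac < 6.5% at baseline". One of four criteria must then be met: HbA1c values, fasting glucose values, a MedDRA diabetes term, or "Initiation of any new concomitant medication for hyperglycemia during the treatment period".
- Diabetic complication: "For patients with medical history of diabetes as specified in Cardiovascular History and Cardiovascular Risk Factors and Medical History CRF pages". The criteria are then listed TEAE terms, an increased dose of a diabetic drug, or "initiation of additional diabetic medication".

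Table 2 gives no e-CRF tick box for either row. SAP 5.8.2 relies on the same appendix: "AESI are defined by SMQ, CMQ, and/or dedicated e-CRF as described in Appendix 10.3".

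SAP 5.8 has a separate rule for analyses by diabetes status, based on history alone: "considering diabetic patients as patients with either type 1 or type 2 diabetes in the medical history e-CRF page".

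Protocol 9.4.3 also defines new onset of diabetes, as a diabetes TEAE or repeated raised HbA1c or fasting glucose. It has no condition on baseline HbA1c. SAP 1.2.3 reports no modifications from the protocol's statistical section.

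**The concern.** The row titles, repeated in SAP 4.8.1.2, present one AESI for patients free of diabetes at baseline and one for patients who have it. A reader of the tables would assume that every treated patient belongs to one or the other. The conditions use different information, however. The first uses history and HbA1c, the second history only. A patient whose diabetes shows only in the baseline HbA1c is too diabetic for the first and not recorded as diabetic for the second.

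Long-term safety is the primary objective, and new onset of diabetes is an AESI named in the protocol. If such a patient has a diabetes TEAE or starts a glucose-lowering drug, following the SAP exactly leaves that event out of both diabetes AESIs. This is the effect of a stated rule, not of missing detail.

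**Working it through.** The plan gives no figure to reproduce, so the check is one of logic.

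**Step 1. Entry conditions, from SAP Table 2.** Let H be a recorded history of diabetes and A the baseline HbA1c in percent.

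- New onset: not H, and A < 6.5
- Diabetic complication: H

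**Step 2. Put every type of patient through both.**

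| History | Baseline HbA1c | New onset | Diabetic complication |
|---|---|---|---|
| No | below 6.5% | yes | no |
| No | 6.5% or more | no | **no** |
| No | missing | not stated | no |
| Yes | any or missing | no | yes |

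Using the values 5.5, 6.4, 6.5, 7.5, 9.0 and missing for A gives 2 × 6 = 12 combinations, 6 of them without history. If a missing value fails the condition A < 6.5, which is the literal reading, 4 of those 6 fall in neither AESI. If a missing value is programmed as meeting it, 3 of 6 still do: 6.5, 7.5 and 9.0. The second row of the table is therefore certain. The third depends on programming, because the missing-baseline rule in SAP 6.3 is given only for PCSVs.

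**Step 3. Is there another way in?** No. Neither row has a tick box, and SAP 5.8.2 points back to Appendix 10.3.

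**Step 4. Can such a patient be enrolled?** For evinacumab-naïve patients, Protocol 6.2.2 criterion 5 excludes a recent diagnosis, and otherwise only "diabetes mellitus or poorly controlled (HbA1c >9%) diabetes". Undiagnosed HbA1c between 6.5% and 9% is not barred. HbA1c is absent from the screening schedules (Protocol Tables 1 and 2) and first appears at the baseline visit in Table 3. SAP 4.1 itself has a baseline HbA1c category of 6.5% or more.

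**Step 5. Size.** The documents give no proportion. Assume that 1% to 3% of patients have no history and a baseline HbA1c of 6.5% or more.

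- All patients: 0.01 × 120 = 1.2 and 0.03 × 120 = 3.6, so about 1 to 4.
- Adolescents: 0.01 × 14 = 0.14 and 0.03 × 14 = 0.42, so fewer than one.

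These are patients in the gap. Only some of them would have an event.

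**Step 6. Check of the remedy.** Define the flag F as H or A ≥ 6.5, with a missing A classified by H. Of the 12 combinations, 6 + 3 = 9 have F true (Diabetic complication) and 3 have F false (5.5, 6.4 and missing, all without history; at risk for new onset). Since 9 + 3 = 12, each combination falls in exactly one AESI.

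**The case against.** The best case against the point is that little is lost. A diabetes or hyperglycaemia AE stays in the TEAE tables (SAP 5.8.1). A new glucose-lowering drug is in the concomitant-medication tables (SAP 5.3). HbA1c is summarised by visit (SAP 5.9). A fasting glucose of 7 mmol/L or more and an HbA1c above 8% are PCSVs with listings (SAP 5.8.3 and 10.4). Investigators must report new-onset diabetes within 24 hours under the protocol's wider definition. A reader might infer that these events vanish from the report; they do not. But none of those outputs is the diabetes AESI analysis, and the gap there remains.

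It is also fair that a patient at 6.5% or more before dosing should not count as new onset. Exclusion from that row is reasonable. The fault is that the other row does not take the patient.

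Several stronger readings are tempting and are not supported:

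- **A rising HbA1c is lost because of the gap.** Diabetic complication has no laboratory criterion, so a rise not reported as an AE would count in neither AESI even after the remedy.
- **Every patient with a missing baseline HbA1c and no history is lost.** The SAP states no rule, HbA1c is scheduled at baseline, and unscheduled values may supply it (SAP 6.5). Nothing shows that missing values are common.
- **The history-only rule in SAP 5.8 distorts results.** The SAP specifies no analysis by diabetes status, and diabetes is not among the subgroups in SAP 5.7.2.
- **Rates are diluted by an all-patient denominator.** SAP 5.8.2 gives no denominator for these AESIs, and the row titles may imply restricted ones.
- **Patients from a previous study face no HbA1c limit.** For those from R1500-CL-1629, baseline is the value before the first double-blind dose of that study, whose entry criteria are not in these documents.

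**Conclusion.** The point holds, confined to the two AESI rows. As written, a patient with no recorded diabetes and a baseline HbA1c of 6.5% or more is excluded from both diabetes AESIs, so a diabetes or hyperglycaemia TEAE or newly started glucose-lowering drug in that patient is counted in neither. This follows from the text of Table 2 alone and needs no clinical assumption.

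The size is unknown and probably small. The figure of about 1 to 4 patients rests entirely on the assumed 1% to 3% of 120. The study is descriptive, so no test or sample size is affected. The correction is worth making because the rule is definite, the AESI belongs to the primary safety evaluation, and the change is trivial.

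**What to change.** 1. In SAP Table 2, define diabetes at baseline by a single flag: a recorded history of diabetes or a baseline HbA1c of 6.5% or more. Classify a patient with missing baseline HbA1c by history.
2. Assign flagged patients to Diabetic complication. All others are at risk for new onset of diabetes.
3. Use the same flag in SAP 5.8 for any analysis by diabetes status, for consistency.
4. Record in SAP 1.2.3 that the baseline HbA1c condition for new onset differs from Protocol 9.4.3.

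The cost is a few sentences and one derived variable, with no new data collection. SAP section 1 allows revision before database lock. One consequence to accept: a patient without history whose baseline HbA1c is missing could have existing diabetes counted as new, which errs towards counting the event.
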